The Efficacy and Safety of Silodosin Singly or Combined with Ningmitai Capsules in the Treatment of Benign Prostatic Hyperplasia (BPH) Complicated with Lower Urinary Tract Symptoms (LUTS) —A Multicenter, Prospective, Randomized, Doubleblind, Positive Controlled Study

Date: September 8, 2022

Research Proposal Summary

Scheme number	NM-22-A-001-YJ-001					
Scheme name	The Efficacy and Safety of Silodosin Capsules Singly or Combined with Ningmitai Capsules in the Treatment of Benign Prostatic Hyperplasia					
Version number/date	Version 1.0, December2, 2021					
sponsor	Shanghai Haitian Pharmaceutical Technology Development Co., Ltd.					
Clinical trial staging	Post-marketing clinical re-evaluation					
test drug	Ningmitai Capsules (Ningmitai [®] , Z20025442), each 0.38g, was produced by Guiyang Xintian Pharmaceutical Co., Ltd.					
	Silodosin Capsules (Qianweitai®, H20213612), each 4mg, was produced by Shanghai Huilun Pharmaceutical Co., Ltd.					
	Tamsulosin Hydrochloride Sustained Release Capsules(H20000681), each0.2mg, was produced by Astellas Pharma Inc.					
	Placebo, Ningmitai capsule simulator, each0.38g, was produced by Guiyang Xintian Pharmaceutical Co., Ltd.					
Indications	Benign Prostatic Hyperplasia with Lower Urinary Tract Symptom					
Test purposes	1.To evaluate the efficacy and safety of Silodosin Capsules alone versus Tamsulosin Hydrochloride Sustained Release Capsules in the treatment of BPH with lower urinary tract symptoms.					
	2.To evaluate the efficacy and safety of Ningmitai Capsules combination with Silodosin Capsules versus Silodosin Capsules alone in the treatment of BPH with lower urinary tract symptoms.					
Research design	A multicenter, prospective, randomized, controlled clinical trial design					
total number	It is planned to complete 312 cases (considering the 20% dropout rate)					
number of research	8					

centers					
Study period	6 months				
research	Diagnostic criteria:				
object	1. Male Subjects aged 60 ~ 80 years, clinically diagnosed as benign prostatic hyperplasia.				
	2. Has an IPSS score ≥ 8 points at Screening and Baseline.				
	3. Has a $4 \le Q_{max} \le 15$ ml/s when urination volume > 150 ml.				
	4. Has a prostate volume (PV) \geq 30 ml by ultrasound examination.				
	5. Subjects who can read, understand, and complete the research questionnaire.				
	6. Subjects willing to participate voluntarily in this clinical trial, give informed consent and sign				
	informed consent.				

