	Exclusion criteria: 1. Subjects with prostate cancer or other malignant tumors.				
	2. Subjects have serum tPSA > 10ng/ml , or $4 \le \text{tPSA} \le 10 \text{ng/ml}$ while fPSA/tPSA < 0.16 times.				
	3. Subjects suffered from other diseases causing dysuria, such as bladder neck spasm, urethral				
	stricture, neurogenic bladder dysfunction, etc.				
	4. Subjects have suffered from acute urinary retention, or complicated with gross hematuria,				
	urinary tract infection, bladder stones, secondary upper urinary tract hydronephrosis, urinary				
	incontinence, renal insufficiency and other subjects that researchers believe meet the surgical				
	indications.				
	5. Subjects have undergone prostate surgery, microwave therapy, urethral dilatation or acute				
	urinary retention catheterization or other invasive procedures.				
	6. Subjects have residual urine volume (PVR) > 100ml, or those who may have urinary retention				
	and need catheterization.				
	7. Subjects who took α receptor blockers, traditional Chinese Medicine or botanical drugs for				
	treating BPH within two weeks before participating this clinical trial.				
	8. Subjects who take 5α reductase inhibitor or other antiandrogen therapy drugs within half a year				
	before participating this clinical trial.				
	9. Subjects who need to take drugs prohibited in this study or adopt prohibited treatment methods				
	during treatment.				
	10. Subjects who Complicated with severe cardiovascular and cerebrovascular diseases, respiratory				
	diseases, blood diseases, liver, and kidney diseases.				
	11. There are significant abnormalities in clinical or laboratory examination indexes of patients,				

such as ALT and AST \geq 2.5 times of the upper limit of reference value, creatinine (Scr) > 1.5 times of the upper limit of reference value, or poor blood glucose control (fasting blood glucose FPG \geq 10 mmol/L).

- 12. Subjects who are allergic to the drugs or ingredients used in the test definitely.
- 13. Any other Subjects in the opinion of researchers is not suitable for inclusion.

Trial grouping and

According to the random sequence generated by computer, eligible patients were randomly assigned to three groups according to 1: 1: 1.

medication

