The Efficacy and Safety of Silodosin Singly or Combined with Ningmitai Capsules in the Treatment of Benign Prostatic Hyperplasia (BPH) Complicated with Lower Urinary Tract Symptoms (LUTS) —A Multicenter, Prospective, Randomized, Double-blind, Positive Controlled Study

Date: September 8, 2022

Statistical analysis Plan

1.Statistical analysis of population:

- (1) **FAS:** According to the basic principle of intentionality analysis (ITT), all the randomized subjects with more than one medication record and effectiveness evaluation were included in the full analysis set. The total analysis set is the main validity evaluation population of this study.
- (2) **PPS:** Include all subjects who have completed the treatment stipulated in the scheme or have not seriously violated the trial scheme. The exact definition of the serious violation scheme will be finalized during the data review. PPS is the secondary analysis population of validity, but if its results are inconsistent with the full analysis set, it is necessary to analyze the inconsistent results in detail.
- (3) **SS:** Defined as all subjects who were randomized and received at least one trial drug treatment. The safety analysis set is the safety evaluation population of this study.

2.Statistical analysis method:

- (1) **General principle:** All statistical analysis shall be processed by SPSS 23.0 and above statistical software, and shall be carried out according to the pre-established statistical analysis plan. Measurement data are described by mean, standard deviation, median, quartile, maximum and minimum. The counting data are described by frequency and percentage. After 12 weeks of treatment, the changes of IPSS scores between Tamsulosin + placebo group and Silodosin + placebo group were compared by non-inferior test, while the changes of IPSS scores between Ningmitai + Silodosin group and Silodosin + placebo group were compared by superior test, and the test levels were $\alpha = 0.025$ (unilateral). Other hypotheses were tested by two-side test with a test level of $\alpha=0.05$, and the secondary index was adjusted by Bonferroni method with a test level of $\alpha=0.0167$.

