- (2) **Balance analysis of baseline value:** Comparability analysis of demographic characteristics, general situation and baseline situation (before treatment) of the two groups of data. Among them, t test or Wilcoxon rank sum test was used for measurement data and grade data, and χ^2 test or Fisher exact probability method was used for classification data.
- (3) **Effectiveness analysis:** Conducted in FAS and PPS at the same time.

① **Main endpoint indicators:** After 12 weeks of treatment, the difference of IPSS score decline and 97.5% CI of the three groups were calculated. If the lower limit of unilateral 97.5% confidence interval of the difference of IPSS score decline between Silodosin + placebo group and Tamsulosin + placebo group is greater than the non-inferiority threshold of 1 (-1 point), then "Silodosin + placebo" is not inferior to "Tamsulosin + placebo" group. If the lower limit of unilateral 97.5% confidence interval of the difference between the IPSS scores of Silodosin + Ningmitai group and Silodosin + placebo group is greater than the superior effect threshold of 2 (0 points), then "Silodosin + Ningmitai" is superior to "Silodosin +

placebo". Subgroup analysis was considered according to whether the NIH-CPSI pain score was ≥ 4 before treatment and the severity of IPSS total score.

②Secondary endpoint index: The changes of IPSS scores, IPSS sub-scores and QoL scores were compared between groups at 1, 2, 4, 8 and 12 weeks after treatment. The changes of Q_{max} , PVR, serum PSA and prostate volume were compared between groups by single factor analysis of variance or Wilcoxon rank sum test. Bonferroni method was used to adjust the test $\alpha = 0.0167$. The clinical progression curve of BPH was drawn by Kaplan-Meier; COX regression model was used to compare the factors affecting the clinical progression of BPH. The proportion of patients with IPSS total score decreased in severity was compared between groups by χ^2 test or Fisher exact probability method.

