	
medicine or decoction containing ephedra.
 
Concomitant drugs allowed during the study period:
 
If the subjects have basic diseases and need to take drugs for a long time, and they are not prohibited drugs in this study, they can continue to use them during the study period.
 
If the subject has adverse reactions, it is up to the researcher to decide whether to use symptomatic treatment drugs.
 
All drugs used at the same time should be recorded and explained in detail on CRF table.

Treatment and follow-up	
Course of treatment: 12 weeks
 
Visit points: screening period, days -28 to 0), after 1 week of treatment (day 7±2), after 2 weeks of treatment (day 14±3), after 4 weeks of treatment (day 28±5), after 8 weeks of treatment (day 56±7), after 12 weeks of treatment (day 84±10).

Research steps	
This trial is divided into two stages: screening period, treatment period and follow-up period.
 
Screening period (days -28 to 0): After signing the informed consent form, the subjects entered the screening period, and made a 24-hour urination diary and screening examination.
 
Treatment and Follow-up period: eligible patients were randomly assigned to three groups according to 1: 1: 1 and received Tamsulosin + placebo, Silodosin + placebo or Silodosin + Ningmitai for 12 weeks. During the treatment period, the subjects' diaries were recorded according to the requirements of the scheme, and they were followed up at 1 week (7±2 days), 2 weeks (14±3), 4 weeks (28±5 days), 8 weeks (56±7 days) and 12 weeks (84±10 days). During the visit, relevant scale scores and laboratory examinations were performed, and the occurrence of adverse events during the follow-up was recorded to evaluate the safety.

study endpoint	
Primary endpoint:
 
International Prostate Symptom Score (IPSS), Changes of scores at the 12th week of treatment compared to the baseline scores.
 
Secondary endpoints:
 
1. IPSS Score
 
① changes of IPSS total score: Changes of IPSS scores at 1, 2, 4 and 8 weeks after treatment compared with baseline scores
 
② Proportion of patients with IPSS total score severity decreased by at least one grade at 12 weeks
 
③ IPSS sub-score: IPSS Stimulation Score at 1, 2, 4, 8, 12 weeks (Sum of Question 2, 4, 7) and

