
Changes of IPSS obstruction score (sum of question 1, 3, 5, 6) compared with baseline.
 
2. Quality of life (QoL) score: Changes in scores at 4, 8 and 12 weeks of treatment compared with baseline
 
3. Maximum urinary flow rate (Q_{max})
 
The change of Q_{max} at 12 weeks of treatment compared with baseline.
 
4. Patient response rate
 
Patient response rate is defined as the proportion of patients whose IPSS total score decreased by $\geq 25\%$ and Q_{max} increased by $\geq 30\%$ compared with baseline value after treatment.
 
5. Residual urine volume (PVR)
 
Changes of PVR at 12 weeks of treatment compared with baseline.
 
6. Prostate specific antigen (PSA)
 
Changes of PSA at 12 weeks of treatment compared with baseline.
 
7. Prostate volume (PV)
 
Changes of PV at 12 weeks of treatment compared with baseline.
 
8. Proportion of patients with BPH clinical progression
 
Clinical progress is defined as the first occurrence of one of the following two conditions during the trial:
 
 ① Acute urinary retention (AUR). ② Clinical diagnosis requires surgical treatment of BPH. 
Subgroup analysis:
 
Patients were grouped according to the following conditions of subjects at baseline, and the therapeutic effect of curative effect indicators was evaluated among different subgroups to determine whether the therapeutic effect was consistent among subgroups:
 
 ① The scores of IPSS were moderate (8-19) and severe (20-35); ② Routine examination of EPS (EPS leukocytes > 4HP or < 4HP. If EPS is not collected after prostate massage, it is not advisable to repeat massage for many times, and it is recommended to take urine after prostate massage for analysis.). ③ Symptoms of chronic prostatitis (NIH-CPSI pain score ≥ 4 and < 4)

security indicators	
The incidence of adverse drug events/reactions was calculated according to the following indicators:
 
1.Vital signs: Blood pressure, heart rate2.Laboratory examination index: Blood routine, Urine routine, liver function (ALT, AST, ALP) and renal function (BUN, Scr).3.Possible adverse drug events/reactions.
--------------------------------	--

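### The unadjusted test of the IPSS grade-drop proportion ignores how far each man starts from the cut-off; it is valid but gives up power, by an amount that depends on assumed inputs

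*SAP*

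**What the plan says.** The protocol lists this endpoint under study endpoint, Secondary endpoints 1②, and the SAP repeats it: "Proportion of patients with IPSS total score severity decreased by at least one grade at 12 weeks". Neither document defines the grades there. The only bands appear under subgroup analysis, item 1: "The scores of IPSS were moderate (8-19) and severe (20-35"). Eligibility requires "Has an IPSS score ≥ 8 points at Screening and Baseline", so every man starts in one of these two bands.

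SAP 2(3)② gives the analysis: "The proportion of patients with IPSS total score decreased in severity was compared between groups by" a chi-square test or the Fisher exact method. No covariate or stratum is named. Baseline severity enters the plan only as a subgroup factor.

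On the error rate, SAP 2(1) says "Other hypotheses were tested by two-side test with a test level of" 0.05, and that "the secondary index was adjusted by Bonferroni method with a test level of" 0.0167. On size, the protocol summary says "It is planned to complete 312 cases (considering the 20% dropout rate"), and under grouping "eligible patients were randomly assigned to three groups according to 1: 1: 1". No power, SD or expected rate is given for any endpoint.

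**The concern.** Success on this endpoint depends on two things: how much a man improves, and how far above the next lower grade he began. The second is known exactly before treatment. A man at 20 succeeds with a 1-point fall to 19. A man at 19 fails with an 11-point fall to 8. The planned test treats this predictable spread as random error.

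What is at stake is efficiency on one secondary endpoint that is already tested at a reduced level. The baseline score is collected anyway, so some of the lost power could be recovered without extra patients or measurements. The obvious remedy, a linear baseline IPSS term, would not do it.

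**Working it through.** **Distance to the next lower grade.** This follows from the plan's bands, taking mild as 7 or below:

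- baseline 8-19: points needed = baseline - 7, so 1 at a score of 8 and 12 at 19;
- baseline 20-35: points needed = baseline - 19, so 1 at a score of 20 and 16 at 35.

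The distance climbs to 12, restarts at 1, and climbs again. A linear baseline term cannot follow that shape.

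**Size and test level, from the documents.** 312 / 3 = 104 per arm; 104 x 0.80 = 83.2, so about 83 completers per arm. 0.05 / 3 = 0.0167. The 312 itself cannot be reproduced, because its inputs are not stated.

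**Assumptions, none from the documents.** Integer baseline about N(17,5) cut to 8-35; mean decline 5 in one arm and 7.2 in the other; SD of the decline 4, 5 or 6; follow-up score limited to 0-35.

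**How strongly distance predicts success.** With mean decline 5, SD 5 and whole-point scores, the chance of falling at least k points is 1 - Φ((k - 0.5 - 5) / 5):

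- k = 1: 1 - Φ(-0.9) = 82%
- k = 6: 1 - Φ(0.1) = 46%
- k = 12: 1 - Φ(1.3) = 10%

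Fitting a separate success rate at each distance, distance explains about 31% of the variance of the binary outcome at SD 4, 23% at SD 5 and 17% at SD 6.

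**Power.** Simulated two-arm comparisons, 83 per arm, two-sided 0.0167. The planned Pearson chi-square is set against a logistic likelihood-ratio test with arm and distance.

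| SD | Chi-square | Adjusted for distance | Gain (points) |
|---|---|---|---|
| 4 | 36% | 53% | 17 |
| 5 | 28% | 38% | 10 |
| 6 | 21% | 28% | 7 |

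Repeat runs agree to within about 2 points. Replacing distance by linear baseline IPSS adds at most about 1 point to the chi-square result.

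**Sensitivity.**

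- True difference of 1 point (decline 5 vs 6): about 7% to 10% at SD 4, 6% to 8% at SD 5 and 5% to 6% at SD 6, a gain of 1 to 3 points.
- 104 per arm, SD 5, decline 5 vs 7.2: about 35% to 47%.
- A wider grid (baseline mean 17-20 and SD 5-6, mean fall 6-8, extra effect 2-3 points, SD 4-6, 83 or 104 per arm), adjusting for distance plus baseline grade: gains of about 3 to 22 points.
- No true difference: rejection between 1.1% and 1.9% across runs for both tests, close to the nominal 1.67%.

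**The case against.** Four points can be made against acting on this.

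**The planned test is sound.** Randomisation makes the unadjusted comparison valid. A chance imbalance in distance between arms is sampling variation that its error rate already covers. A reader might infer bias or a false-positive problem; neither the design nor the simulations support that. This stands in full.

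**The endpoint carries little of the inference.** The primary endpoint is the continuous week-12 change, which credits a fall from 19 to 8 with its full 11 points. With a 2.2-point difference and SD 5, the standard error is 5 x √(2/83) = 0.776 and 2.2 / 0.776 = 2.83, which gives an unadjusted t-test about 80% power at one-sided 0.025. The grade-drop test stays well short of that even after adjustment. This also stands, and it limits the importance of the point.

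**A simple comparison of proportions is a legitimate target.** A logistic model gives a conditional odds ratio, which is a different quantity. This stands, and is why the raw proportions and their difference must still be reported.

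**Any category endpoint treats 20 to 19 and 19 to 8 this way.** Correct. Adjustment leaves both men coded as they are now, so the examples show why distance predicts success; they are not a defect that the adjustment repairs.

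A reader might also infer that the endpoint mostly reflects where men started. At about 17% to 31% of outcome variance, distance is a large known part but not the majority. What remains is the efficiency argument, which none of these objections removes.

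**Conclusion.** The concern holds as a minor, optional improvement in efficiency. That the required fall runs from 1 to 16 points, and that the planned test ignores it, follows from the documents once mild is read as 7 or below and the subgroup bands are taken to define this endpoint. Both readings are reasonable, but the plan does not state them.

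The size is less secure. Gains of about 7 to 17 points at SD 6 to 4 rest wholly on assumed inputs and a 2.2-point difference, so they should not be read as a property of this plan. The gain shrinks quickly with the effect. The SAP frames silodosin against tamsulosin as a non-inferiority question; if those two arms barely differ, there is almost nothing to recover in that comparison. No conclusion about the primary endpoint is affected.

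**What to change.** In SAP 2(3)②, before unblinding:

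1. State the grade bands for this endpoint, including the mild band.
2. Compare arms by logistic regression, using the likelihood-ratio test at the level already set, with arm and one covariate: points needed to reach the next lower grade (baseline - 7 if 8-19, baseline - 19 if 20-35). Linear baseline IPSS is not a substitute.
3. Report the raw proportions and their difference beside the odds ratio.

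The cost is about one sentence, the stated bands and one variable derived from data already collected; SPSS, the software the SAP names, can fit the model. The downside is that the odds ratio is conditional on distance, so it must be labelled as such and not read as the contrast of the raw proportions.

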Course of treatment: 12 weeks

Visit points: screening period, days -28 to 0), after 1 week of treatment (day 7 ± 2), after 2 weeks of treatment (day 14 ± 3), after 4 weeks of treatment (day 28 ± 5), after 8 weeks of treatment (day 56 ± 7), after 12 weeks of treatment (day 84 ± 10).

Research steps

This trial is divided into two stages: screening period, treatment period and follow-up period.

Screening period (days -28 to 0): After signing the informed consent form, the subjects entered the screening period, and made a 24-hour urination diary and screening examination.

Treatment and Follow-up period: eligible patients were randomly assigned to three groups according to 1: 1: 1 and received Tamsulosin + placebo, Silodosin + placebo or Silodosin + Ningmitai for 12 weeks. During the treatment period, the subjects' diaries were recorded according to the requirements of the scheme, and they were followed up at 1 week (7 ± 2 days), 2 weeks (14 ± 3), 4 weeks (28 ± 5 days), 8 weeks (56 ± 7 days) and 12 weeks (84 ± 10 days). During the visit, relevant scale scores and laboratory examinations were performed, and the occurrence of adverse events during the follow-up was recorded to evaluate the safety.

study endpoint

Primary endpoint:

International Prostate Symptom Score (IPSS), Changes of scores at the 12th week of treatment compared to the baseline scores.

Secondary endpoints:

1.IPSS Score

- ①changes of IPSS total score: Changes of IPSS scores at 1, 2, 4 and 8 weeks after treatment compared with baseline scores
- ②Proportion of patients with IPSS total score severity decreased by at least one grade at 12 weeks
- ③IPSS sub-score: IPSS Stimulation Score at 1, 2, 4, 8, 12 weeks (Sum of Question 2, 4, 7) and

Changes of IPSS obstruction score (sum of question 1, 3, 5, 6) compared with baseline.

- 2.Quality of life (QoL) score: Changes in scores at 4, 8 and 12 weeks of treatment compared with baseline
- 3. Maximum urinary flow rate (Q_{max})

The change of Q_{max} at 12 weeks of treatment compared with baseline.

4. Patient response rate

Patient response rate is defined as the proportion of patients whose IPSS total score decreased by \geq 25% and Q_{max} .

increased by $\geq 30\%$ compared with baseline value after treatment.

5. Residual urine volume (PVR)

Changes of PVR at 12 weeks of treatment compared with baseline.

6. Prostate specific antigen (PSA)

Changes of PSA at 12 weeks of treatment compared with baseline.

7. Prostate volume (PV)

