(4) Security analysis: To evaluate the safety of SS population. The data of safety evaluation include the adverse events observed during the trial and the changes of laboratory examination data before and after treatment. Descriptive statistics were used for adverse events, and the total incidence of adverse events and the incidence of various adverse events were compared among each group. In addition to comparing the average data before and after treatment, the laboratory examination data mainly analyzed and listed the specific situation of normal cases before treatment and abnormal cases after treatment or abnormal cases before treatment and abnormal cases after treatment.

centers	
Study period	6 months
research	Diagnostic criteria:
object	
 1. Male Subjects aged 60 ~ 80 years, clinically diagnosed as benign prostatic hyperplasia. 2. Has an IPSS score ≥ 8 points at Screening and Baseline. 3. Has a $4 \leq Q_{\max} \leq 15$ ml/s when urination volume > 150 ml. 4. Has a prostate volume (PV) ≥ 30 ml by ultrasound examination. 5. Subjects who can read, understand, and complete the research questionnaire. 6. Subjects willing to participate voluntarily in this clinical trial, give informed consent and sign informed consent.
	Exclusion criteria:

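### The planned laboratory analysis is ungraded and states no comparison by arm, so marked worsening from a raised baseline shares a class with stable or improving mild abnormality

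*SAP*

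**What the plan says.** SAP section 2(4), Security analysis, is the whole laboratory plan. Its laboratory data are "the changes of laboratory examination data before and after treatment". It names two summaries. The first is a comparison of averages ("In addition to comparing the average data before and after treatment"). The second is case-based, an analysis and listing of "normal cases before treatment and abnormal cases after treatment or abnormal cases before treatment and abnormal cases after treatment". The section does not define or grade abnormality. It gives no band in multiples of ULN, no multiple of baseline, no worst on-treatment value and no by-visit summary.

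The only comparison between arms stated in that section concerns adverse events: "the total incidence of adverse events and the incidence of various adverse events were compared among each group".

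Three other places bear on the point:
- Protocol, Exclusion criteria, item 11 sets the entry limits for ALT and AST, and for creatinine: "2.5 times of the upper limit of reference value, creatinine (Scr) > 1.5 times of the upper limit of reference value". Men with raised values short of those limits may enter.
- Protocol, Research steps, says of the follow-up visits: "During the visit, relevant scale scores and laboratory examinations were performed". It does not say which of weeks 1, 2, 4, 8 and 12 include blood tests.
- SAP section 2(1) plans median, quartiles, maximum and minimum as well as the mean for measurement data.

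**The concern.** Both study purposes in the Protocol summary cover safety as well as efficacy, and the second asks what Ningmitai adds to silodosin. For liver and renal function, that means seeing how many men in each arm worsened materially. A two-state label cannot show this when men may enter already abnormal: once a man is abnormal at baseline, he stays in one class whether his value quadruples or falls almost to normal. The same holds at the lower end, where a man moving from normal to just above ULN is classed with one who moves from normal to many times ULN. Two arms could therefore show equal counts of abnormal cases and similar averages while one has several marked rises.

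**Working it through.** The plan gives no laboratory figure to reproduce, so this is a reading of the text followed by an illustration.

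**1. What the classes separate.** The ALT courses below are hypothetical. The first two men are eligible on the natural reading of exclusion 11, because 2 x ULN is below 2.5 x ULN.

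| ALT, baseline to worst value | Class in SAP 2(4) | Cell in a banded shift table |
|---|---|---|
| 2 x to 8 x ULN | abnormal to abnormal | middle band to top band |
| 2 x to 1.2 x ULN | abnormal to abnormal | middle to middle |
| normal to 1.1 x ULN | normal to abnormal | bottom to middle |
| normal to 8 x ULN | normal to abnormal | bottom to top |

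Bands: at or below ULN; above ULN to below 2.5 x ULN; 2.5 x ULN or more. The planned classes merge the men in pairs; the banded table separates them.

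**2. Routes to an arm comparison.** SAP 2(4) compares adverse event incidence among the arms. The Protocol's security indicators item ties adverse event incidence to indicators that include ALT, AST, ALP, BUN and Scr. A laboratory rise recorded as an adverse event would therefore be compared by arm. Neither document says when a laboratory value becomes an adverse event, so this route is open but not assured.

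**3. Whether averages fill the gap.** Inputs: 312 men allocated 1:1:1 (Protocol, total number and Trial grouping), so 312/3 = 104 per arm. The remaining inputs are assumptions, not from the documents: k men in one arm rise from 2 x to 6 x ULN, the change SD in everyone else is s = 0.3 to 0.5 x ULN, and the test is two-sided at 5%.
- Shift in arm mean = 4k/104.
- SD in the affected arm = √[s² + 16(k/104)(1 − k/104)].
- SE of the difference = √[(SD² + s²)/104].
- Power ≈ Φ(shift/SE − 1.96).

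For k = 3 the shift is 12/104 = 0.115. With s = 0.3, SD² = 0.09 + 0.448 = 0.538, SE = √(0.628/104) = 0.078, the ratio is 1.48 and power is 32%. With s = 0.5, the ratio is 1.21 and power is 23%.

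| k | Shift (x ULN) | Power, s = 0.5 to 0.3 |
|---|---|---|
| 1 | 0.04 | 7% to 10% |
| 3 | 0.12 | 23% to 32% |
| 5 | 0.19 | 42% to 54% |

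This is generous to the plan, which describes before/after averages and does not state a between-arm test of them. In raw units, one man with an assumed 300 U/L rise moves his arm mean by 300/104 = 2.9 U/L.

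**4. What a graded count can do.** Fisher's exact test on k/104 against 0/104 gives p = 0.25 for k = 3, 0.06 for k = 5 and 0.03 for k = 6. A graded table would be read descriptively.

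**5. A peak that resolves.** This is missed only if two things hold: blood is drawn at intermediate visits, and the after-treatment value means the final visit. The documents settle neither.

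**The case against.** The strongest reply is that the plan already offers several places where a marked rise would appear. Adverse event incidence is compared among arms and is linked to the laboratory indices. The case listing covers the specifics of each abnormal case, so a rise from 2 x to 8 x ULN should be visible individually. The maximum in SAP 2(1) would show an extreme value among the data summarised. All of this stands, and it rules out a reading that a reader might infer: that such worsening can appear in no arm comparison at all. What remains is that the adverse event route depends on a judgement with no stated criterion, and that neither a listing nor a maximum counts, by arm, the men who worsened markedly.

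A second reply concerns timing, and it also stands. The Protocol labels every on-treatment visit as after so many weeks of treatment, so an after-treatment abnormality may include any post-baseline sample. If blood is drawn only at baseline and week 12, there is no scheduled mid-treatment value to miss. The resolved-peak point must stay conditional.

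A reader might also infer that men who leave early drop out of the laboratory analysis. The documents do not support this. The safety set in SAP section 1(3) takes in every randomised man who received trial drug, no rule removes those without a final sample, and the 20% dropout allowance is a planning figure rather than a count of missing laboratory values.

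Finally, graded counts have little power at this size. That is true, but the purpose of the table is to make the pattern visible by arm, not to test it.

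**Conclusion.** The gap is real but limited. As written, SAP 2(4) has no graded laboratory summary and states no laboratory comparison by arm. Because exclusion 11 admits mildly raised baselines, marked worsening and improvement that stops short of normal share one class. Such worsening is compared between arms only if it is recorded as an adverse event; otherwise it appears only in listings and extremes.

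The size cannot be taken from the documents, which give no laboratory SDs and no expected rates. The 23% to 32% power for three marked rises rests on the assumed SDs and on 104 men per arm. The classification problem rests only on the text and on reading exclusion 11 as applying to either enzyme. The literal wording joins ALT with AST, and so might admit a man with one enzyme above the limit, which would make the problem larger. The primary endpoint, sample size and alpha are unaffected; the weakness lies in the safety half of the two study purposes.

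**What to change.** In SAP 2(4), add a shift table by arm in the SS, with baseline category against worst post-baseline value, using every post-baseline sample actually collected. Use cut-offs the protocol already contains:
- ALT and AST, each separately: at or below ULN; above ULN to below 2.5 x ULN; 2.5 x ULN or more.
- Creatinine: at or below ULN; above ULN to 1.5 x ULN; above 1.5 x ULN.
- Other indices (ALP, BUN, blood and urine routine): normal, abnormal, or worsened from baseline, by arm.

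Keep the case listing. The top band is open-ended, so 2.6 x and 8 x ULN share it, and the listing is needed to show the size of changes there. State that the table is descriptive. On the natural reading of exclusion 11, no man is eligible with a screening value in the top band, so entries there will generally be new rises on treatment.

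The cost is SAP wording and one standard table. It needs no extra samples and changes neither alpha nor sample size. The downside is that taking the worst value shows somewhat more abnormalities in every arm than a single after-treatment value would. If blood turns out to be drawn only at baseline and week 12, the table still separates worsening from improvement, but the worst value is then simply the week-12 value for scheduled samples.
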